7.5.1.2 Sensitivity analysis of the key secondary endpoints

Sensitivity analysis for the key secondary endpoint will include

- a mixed model repeated measure analysis without imputation of missing values (OC-AD).
- a mixed model repeated measure analysis restricted to on treatment values (OC-OT).

The model will include visit-by-treatment interaction and baseline-by-visit interaction. An unstructured covariance structure will be used to model the within-patient errors. Descriptive statistics will be calculated for the value at visit and change from baseline based on OC-AD on the randomised set and based on OC-OT on the treated set.

The primary analysis will be repeated restricted to patients in sensitivity analysis sets SensRS2 and SensRS3.

7.5.1.3 Subgroup analysis of the key secondary endpoints

The primary analysis of the key secondary endpoints will be repeated for each subgroup as defined in [Table 6.4: 1](#). A forest plot summarising all subgroup analyses will be shown.

7.5.1.4 Further exploratory analyses of the key secondary endpoints

A minimal clinically meaningful within-patient change in scores (i.e. responder threshold) will be estimated from the trial population (both treatment groups pooled) for KCCQ-TSS and CHQ-SAS dyspnea as described in [Appendix 9.3](#).

A responder analysis using a chi-square test will be evaluated in addition. The response threshold will be determined as defined in [Appendix 9.3](#).

An empirical cumulative distribution function of descriptive change from baseline to week 12 by treatment group on OC-AD on the randomised set will be shown.

7.5.2 Other Secondary endpoints

Other secondary endpoints will not be part of the testing hierarchy. No correction for multiple testing of the other secondary endpoints will be made.

Change from baseline to week 6 in exercise capacity as measured by the distance walked in 6 minutes will be evaluated using the same model as for the primary endpoint. If no 6MWTD is available at week 6, an imputed value as defined in [Section 6.6](#) will be used.

All other secondary endpoints will take into account all data, regardless of whether the patient was on treatment or not, and without imputation of missing values (OC-AD).

The other continuous endpoints are generally analysed in an MMRM, including visit-by-treatment interaction and baseline-by-visit interaction. An unstructured covariance structure will be used to model the within-patient errors. The MMRM analyses will also be shown graphically.

Descriptive statistics will be calculated for the value at visit and change from baseline.

Shift from baseline score to 12 week score will be tabulated descriptively for single items collected in the context of the clinical congestion score (dyspnea, orthopnea, fatigue, jugular venous distension, rales and edema).

The endpoint “Change from baseline in NT-proBNP at week 12” (after log-transformation) will be evaluated using an MMRM analysis over time with baseline log-transformed NT-proBNP by visit interaction and visit by treatment interaction as covariates without imputation of missing values. Estimates obtained from the model will then be back-transformed and reported on the original scale. The MMRM analyses will also be shown graphically.

Proportion of patients in every category of global impression of change at week 12 will be evaluated using Cochran-Mantel-Haenszel test on the difference in mean treatment scores, using modified ridit scores.

Proportions of patients categorised by the difference in scores between baseline and week 12 in patient global impression of severity score will be evaluated using a Cochran-Mantel-Haenszel test on the difference in mean treatment scores, using modified ridit scores. Difference in score will be defined as the number of categories improved/deteriorated from baseline. Shift from baseline score to 12 week score will be tabulated descriptively.

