7.3.2 Secondary endpoint analyses

Key secondary endpoints

Both key secondary endpoints ‘Change from baseline to week 12 in heart failure symptoms as measured by the KCCQ TSS’ and ‘Change from baseline to week 12 in CHQ-SAS dyspnea score’ will be evaluated using a normal approximation of the Wilcoxon rank test using the randomized set. For estimation of effect the non-parametric Hodges-Lehmann estimate for the median difference will be calculated.

Change from baseline in both scores will be defined as the endpoint value at week 12 minus the last available endpoint value before start of randomised trial medication.

If no questionnaire is available at week 12, an imputed value as defined similar to the imputation for the primary endpoint will be used.

Sensitivity analysis for the key secondary endpoint will include using a mixed model repeated measure analysis with baseline of the key secondary endpoint as a covariate without imputation of missing values.

Other secondary endpoints

Change from baseline to week 6 in exercise capacity as measured by the distance walked in 6 minutes will be evaluated using the same model as for the primary endpoint.

Change from baseline of Clinical Congestion Score at week 12 will be evaluated using a mixed model repeated measure analysis (MMRM) analysis over time. The model will include the factor treatment and the linear covariate of baseline Clinical Congestion Score.

Proportion of patients in every category of global impression of change at week 12 will be evaluated using Cochran-Mantel-Haenszel test. Details on combining categories if the proportion of patients in one of the categories is small will be given in the TSAP.

Proportions of patients categorized by the shift in scores between baseline and week 12 in patient global impression of severity score will be evaluated using Cochran-Mantel-Haenszel test. Details on combining categories if the proportion of patients in one of the categories is small will be given in the TSAP.

The endpoint “Change from baseline in NT-proBNP at week 12” (after log-transformation) will be evaluated using a MMRM analysis over time with baseline log-transformed NT-proBNP as a covariate without imputation of missing values.

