7.6 RANDOMISATION

The trial will be performed as a double-blind design with respect to placebo and empagliflozin. Patients will be randomised to the trial treatments in a 1:1 ratio. No stratification will be performed in this trial.

Patients will be randomised in blocks to double-blind treatment via an IRT system. Approximately equal numbers of patients will be randomised to each treatment group.

BI will arrange for the randomisation and the packaging and labelling of trial medication. The randomisation list will be generated using a validated system, which involves a pseudo-random number generator so that the resulting treatment will be both reproducible and non-predictable. The block size will be documented in the Clinical Trial Report. Access to the codes will be controlled and documented.

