7.7 DETERMINATION OF SAMPLE SIZE

In clinical studies, 30-50 meters have been variably reported as a meaningful distance achieved as a result of therapy [[R17-1227](#)].

The standard deviation (SD) of 72 m is assumed for sample size considerations of this trial [[R17-1225](#)]. The risk of observing a higher SD in this trial will be mitigated by using duplicate measurements of 6MWT at baseline, Week 6 and Week 12 [[R17-2791](#)]. For non-missing values a normal distribution for change from baseline in distance walked in 6 minutes is assumed in all below sample size estimations.

The trial is designed to achieve a power of 90% for a two sided test at level $\alpha = 0.05$ to detect a difference between empagliflozin and placebo.

Using a normal distribution to calculate the probability that an observation X in Empagliflozin group will be less than an observation Y in the control group under the alternative, the following table presents the number of required evaluable patients for different assumed means of absolute difference in distance walked within 6 minutes as obtained by using the Wilcoxon sample size estimation procedure from commercial software nQuery Advisor® 7.0 statistical package by Statistical Solutions Ltd.

Table 7.7: 1 Sample size calculation

True treatment difference in distance walked in 6 minutes	SD	P(X<Y)	Required number of patients per group
30 m	72 m	0.384	131
40 m	72 m	0.347	76
50 m	72 m	0.312	50

A true treatment difference of 30 m is used as a conservative measure for sample size calculation to ensure that the study could detect the lowest effect size reported to be meaningful.

Therefore, a total of 131 evaluable patients per group are needed in order show a significant result for a two-sided test at level $\alpha = 0.05$ with a power of 90% not considering missing data.

To assess the impact of missing data a simulation with 100000 iterations was performed. A normal distribution for 6MWT distance was assumed and a total of 5%, 8% and 10% patients imputed to worst case as outlined in [section 7.5](#) in each treatment group were investigated. The results are summarized in [table 7.7: 2](#).

Table 7.7: 2 Simulation of imputation rules

N per group	Simulated true treatment difference for non-missing data [mean \pm SD]	Percentage of missing data imputed to worst case	Power
150	30 \pm 72	5%	90%
150	30 \pm 72	8%	87%
150	30 \pm 72	10%	85%

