Therefore, a total of 150 patients per treatment group will allow for a drop-out and imputation of about 5% of the patients in order to show a significant result for a two-sided test at level $\alpha = 0.05$ with a power of 90%. With a drop-out rate of 10%, a total of 150 patients per treatment group would still yield a power of 85%.

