7.6.2 Ordinal endpoints

The following endpoints will be evaluated using the same models as defined for the corresponding secondary endpoints:

- Change from baseline in Patient Global Impression of Severity of Heart Failure Symptoms at week 6.
- Change from baseline in Patient Global Impression of Severity of Dyspnea at week 6.
- Patient Global Impression of Change in Heart Failure Symptoms at week 6.

- Patient Global Impression of Change in Dyspnea at week 6.
- Change from baseline in Clinician Global Impression of Severity of Chronic Heart Failure (CHF) at Week 6 and week 12
- Clinician Global Impression of Change in CHF Severity at Week 6 and week 12

Frequencies and proportions of patients categorised descriptively by the

- shift in NYHA class from baseline to week 6 and to week 12.

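### The tests of change in PGI-S and CGI-S name no stratification variable; stratifying by the item's baseline category would gain efficiency at almost no cost

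*SAP*

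**What the plan says.** Protocol 7.3.2 plans a CMH test on "Proportions of patients categorized by the shift in scores between baseline and week 12 in patient global impression of severity score" and names no stratification factor. SAP 7.5.2 adds that the test compares mean scores using modified ridits, and defines the response: "Difference in score will be defined as the number of categories improved/deteriorated from baseline". It also asks for a descriptive shift table.

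SAP 7.6.2 extends this to PGI-S at week 6 and CGI-S at weeks 6 and 12: "The following endpoints will be evaluated using the same models as defined for the corresponding secondary endpoints". Protocol 7.3.3, which covers these further endpoints, names no stratum either. Randomisation supplies none by default, since Protocol 7.6 says "No stratification will be performed in this trial".

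That the test has one stratum is therefore the natural reading, but it rests on silence. Neither document says outright that the test is unstratified.

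For comparison, SAP 7.5.2 also states "The other continuous endpoints are generally analysed in an MMRM", with a baseline-by-visit term. That covers the Clinical Congestion Score and NT-proBNP.

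PGI-S and CGI-S each have five categories (Protocol 5.1.9, 5.1.10 and 5.1.12), and the flow chart schedules them at Visit 2. SAP 7.5.2 analyses PGI-S on observed data without imputation, as SAP 7.6 does for CGI-S.

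**The concern.** On a short bounded scale the room for change depends on where the patient starts. A patient in the best category can only stay or worsen. A patient in a poor category tends to look better next time, because part of a poor rating is occasion noise. Neither source of variation comes from treatment. A one-stratum test ranks all patients together on categories changed, so this variation enters its variance. A test stratified by baseline category compares like with like and removes it.

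At stake is the sensitivity of two named secondary endpoints (PGI-S at week 12) and of the further endpoints that inherit the test. They will be reported with p-values, and the baseline category that would sharpen them is already collected. A second, practical matter is that silence about the strata leaves a choice to the programmer.

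**Working it through.** **1. The plan's own figures.** There are none for PGI-S or CGI-S. The nearest are those for the primary Wilcoxon test in Protocol 7.7, a rank test of the same family, so they serve as a check on method.

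- Noether: n per group = (z₀.₉₇₅ + z₀.₉₀)² / [6(p − 0.5)²], with p = Φ(−δ/(SD·√2)).
- For δ = 30 m and SD = 72 m: p = Φ(−0.295) = 0.384, and n = 10.51 / [6 × 0.1159²] = 130.5, so 131 as stated. For 40 m and 50 m the formula gives 76 and 50, also as stated.
- Simulated power at 150 per group with fixed numbers of worst-ranked patients: 89.9% (7 missing) and 90.1% (8), 87.1% (12) and 84.8% (15), against the stated 90%, 87% and 85%.

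**2. Inputs.**

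- From the documents: two-sided 5%, 1:1 allocation, no strata, five categories. On missing data, Protocol 7.7 says "a total of 150 patients per treatment group will allow for a drop-out and imputation of about 5% of the patients". With no imputation for these items, 150 × 0.95 = 142.5, so about 142 observed per arm.
- Assumed, because the documents are silent: baseline distribution, latent treatment effect (0.2 to 0.4 SD), and baseline to week 12 latent correlation ρ (0.3 to 0.85).

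**3. Analytic expectation.** For a continuous score with equal variance σ² at both visits, the variance of change is 2σ²(1 − ρ), and the variance after adjusting for baseline is σ²(1 − ρ²). The ratio is (1 + ρ)/2. At ρ = 0.5 it is 0.75, so adjustment is worth 1/0.75 = 1.33 times the patients. A change-score test with 50% power (noncentrality 1.96) would move to 1.96 × √1.333 = 2.263, giving Φ(2.263 − 1.96) = 61.9%, a gain of 11.9 points. The same step gives 18.1 points at ρ = 0.3, 6.6 at 0.7 and 3.1 at 0.85. No floor enters this calculation.

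**4. Simulation of the actual test.** Bivariate-normal latent severity was cut into five categories, with 142 per arm and 2,500 runs per cell. The CMH mean-score test with modified ridits on categories changed was run in one stratum and then stratified by baseline category (van Elteren form). Power at latent effect 0.3 SD, by assumed baseline percentages in categories 1 to 5:

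| ρ | 5/35/45/13/2 | 15/30/30/18/7 | 2/28/60/9/1 |
|---|---|---|---|
| 0.3 | 45.8% to 64.8% | 46.3% to 69.0% | 44.5% to 62.7% |
| 0.5 | 57.8% to 72.4% | 57.2% to 74.0% | 53.5% to 66.9% |
| 0.7 | 73.8% to 82.1% | 74.2% to 85.6% | 66.7% to 75.3% |
| 0.85 | 88.0% to 92.9% | 93.2% to 96.7% | 82.1% to 86.2% |

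Range of gains over effects 0.2, 0.3 and 0.4 SD and all three distributions:

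- ρ = 0.3: +8.6 to +22.7 points
- ρ = 0.5: +7.5 to +16.8
- ρ = 0.7: +4.0 to +11.4
- ρ = 0.85: +0.4 to +8.2

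No cell showed a loss. Type I error was 4.8 to 5.0% for one test and 5.0 to 5.2% for the other.

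A separate simulation at 150 per arm, with baselines 5/25/45/20/5 and 10/35/40/13/2, agrees. At effect 0.30 SD it gave 58–61% against 74–75% (ρ = 0.5), 77–78% against 86–87% (ρ = 0.7) and 90% against 93% (ρ = 0.8).

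**5. Is it the floor?** Gains at effect 0.3 SD for ρ = 0.3 / 0.5 / 0.7:

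| Setting | Gain (points) |
|---|---|
| Full sample, 5% in category 1 | 19.1 / 14.2 / 9.7 |
| Category 1 patients dropped | 17.6 / 13.4 / 7.4 |
| Nobody in category 1 at baseline | 16.2 / 11.8 / 8.5 |
| 15% in category 1 with no treatment effect | 17.3 / 12.2 / 8.6 |

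With nobody at the floor, 16.2/19.1 = 85%, 11.8/14.2 = 83% and 8.5/9.7 = 88% of the gain remains. Regression to the mean is the main source. A variant with 0/40/45/13/2, in which category 1 could not be reached at week 12 either, gave gains up to 27.7 points. It describes a four-category scale with 40% already at its best level, so it is left out of the range.

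**The case against.** The strongest reply is that unadjusted rank tests on change are this trial's chosen approach. The primary endpoint and both key secondary endpoints use a Wilcoxon test on change from baseline. So does 6MWT at week 6, which sits in SAP 7.5.2 beside PGI-S. A reader might infer that only the severity items ignore baseline. The documents do not support that: the mean-score CMH on PGI-S change is the ordinal counterpart of the primary test. What does stand is narrower. The 6MWT and key secondary endpoints also have a baseline-adjusted MMRM as sensitivity analysis (SAP 7.4.2 and 7.5.1.2), and 6MWT has an adjusted rank analysis if the baseline means differ by more than 15 m. PGI-S and CGI-S have no baseline-adjusted test.

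Second, the endpoints are exploratory and outside the hierarchy (Protocol 7.2), and no power was promised for them. This is correct and limits the priority.

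Third, a reader might infer that a chance imbalance in baseline severity makes the test invalid. It does not. The change score already subtracts baseline, only a residual regression effect remains, and the null distribution covers it. Baseline PGI-S is also displayed by category (SAP 6.4), and shifts are tabulated.

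Fourth, entry requires NYHA class II to IV, so few patients may start at the best level; the documents give no share. This weakens any argument built on the floor, but step 5 shows that most of the gain does not depend on it.

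**Conclusion.** The point holds as one of efficiency and specification. As written, PGI-S and CGI-S change are tested in a single stratum on a raw change score. The test keeps its level, and no confirmatory conclusion changes.

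The size is conditional. With 142 to 150 per arm, latent effect 0.2 to 0.4 SD and ρ of 0.3 to 0.85, stratifying by baseline category gains about 0 to 23 power points, roughly 4 to 17 at ρ of 0.5 to 0.7. A reader might take some such figure as a property of the plan. It is not one, because every input specific to these items is assumed. The simulations also assume a latent normal model with a common effect, apart from the check with an inert category 1. Within those assumptions the direction was the same throughout. This is a free improvement of minor priority.

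**What to change.** In SAP 7.5.2, state that the CMH mean-score test with modified ridit scores on PGI-S change is stratified by the baseline category of the same item, and that sparse baseline categories are merged at the blinded report planning meeting before unblinding. SAP 7.6.2 then carries this to PGI-S at week 6 and to CGI-S by reference. Keep the shift tables. If an unstratified test is really intended, say so.

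The cost is one sentence and one stratification variable in the procedure call. No patient is lost through the stratum, since a patient without a baseline rating has no change score anyway. Merging is needed because a stratum with patients from one arm only contributes nothing; SAP 6.4 already allows small subgroups to be combined at that meeting.

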7.6 FURTHER ENDPOINTS

All further endpoints will take into account all data, regardless of whether the patient was on treatment or not, and without imputation of missing values (OC-AD).

7.6.1 Binary endpoints

For the following binary endpoints descriptive analyses will be complemented by an exploratory chi-square test to compare response between treatment groups.

- Increase in 6MWT ≥ 30 m from baseline at week 12
- Response in KCCQ domains at week 12, as defined in [Section 5.3](#). A forest plot of response at week 12 for each domain by treatment will be shown.
- Response in CHQ domains at week 12, as defined in [Section 5.3](#). A forest plot of response at week 12 for each domain by treatment will be shown.

Descriptive statistics are planned for all other binary endpoints:

- Occurrence of HHF and Cardiovascular (CV) death
- Occurrence of all-cause mortality
- Occurrence of CV death
- Occurrence of all-cause hospitalisation (first and recurrent)
- Occurrence of hospitalisation for HF (first and recurrent)
- Occurrence of all-cause emergency room visits (first and recurrent)
- Emergency room visit for HF (requires use of i.v. diuretics; first and recurrent)
- Occurrence of unscheduled outpatient visit (first and recurrent)
- Intensification of diuretic therapy (adding a new diuretic, increase of dose)
- Occurrence of MI (fatal or non-fatal)
- Occurrence of Stroke (fatal or non-fatal)
- Occurrence of TIA

7.6.2 Ordinal endpoints

The following endpoints will be evaluated using the same models as defined for the corresponding secondary endpoints:

- Change from baseline in Patient Global Impression of Severity of Heart Failure Symptoms at week 6.
- Change from baseline in Patient Global Impression of Severity of Dyspnea at week 6.
- Patient Global Impression of Change in Heart Failure Symptoms at week 6.

- Patient Global Impression of Change in Dyspnea at week 6.
- Change from baseline in Clinician Global Impression of Severity of Chronic Heart Failure (CHF) at Week 6 and week 12
- Clinician Global Impression of Change in CHF Severity at Week 6 and week 12

Frequencies and proportions of patients categorised descriptively by the

- shift in NYHA class from baseline to week 6 and to week 12.

7.6.3 Continuous endpoints

Further continuous endpoints are generally analysed in a mixed model with repeated measures (MMRM), including visit-by-treatment interaction and baseline-by-visit interaction. An unstructured covariance structure will be used to model the within-patient errors. The MMRM analyses will also be shown graphically.

Descriptive statistics will be calculated for the value at visit and change from baseline.

- Change from baseline in KCCQ overall summary score, CSS, and individual domains at Week 6 and week 12
- Change from baseline in CHQ individual domains at week 6 and week 12
- Change from baseline in SBP at Week 6 and week 12
- Change from baseline in DBP at Week 6 and week 12

The following endpoint is assessed as part of the main analysis or sensitivity analysis of the corresponding secondary endpoint:

- Change from baseline in KCCQ TSS at Week 6
- Change from baseline in CHQ-SAS dyspnea at Week 6
- Change from baseline in Clinical Congestion Score at week 6.
- Change from baseline in NT-proBNP at week 6.

Since bodyweight is only measured at baseline and week 12, an ANCOVA model will be presented including baseline weight as a covariate.

Descriptive statistics are planned for:

- Change from baseline to week 6 and week 12 in patient-rated assessment of dyspnea and fatigue by the Borg scale as part of the 6MWT

For the following parameters measured at the follow-up visit, additionally descriptive statistics at baseline, last value on treatment and follow-up will be presented for patients with valid measurements at all three timepoints. .

- SBP
- DBP

7.7 EXTENT OF EXPOSURE

Descriptive statistics tables based on the TS with mean, SD, SE, quartiles, median and range of the number of days a patient was on treatment will be provided. These tables will also provide the sum-total of the time (in years) that all patients were on treatment.

Frequency tables of number and percentage of patients belonging to categorical ranges of exposure weeks will be provided as well. Following are the categories of exposure-ranges (in weeks): ≥ 0 weeks, ≥ 4 weeks, ≥ 8 weeks, ≥ 11 weeks.

